6.3 Statistical Methods

Data preparation and balance tests. To prepare the data, we will first examine all scales to ensure adequate internal consistency (i.e., Cronbach's alpha > 0.70), dropping items as needed to improve consistency. If we are unable to achieve adequate internal consistency by dropping items, we may exclude the unreliable scales from analyses (e.g., not analyze treatment effects on these outcomes).

Next, we will conduct balance tests. Specifically, we will report participants' age, gender, sexual orientation, Hispanic ethnicity, race, educational attainment, health literacy, household income, usual sugar-sweetened beverage consumption, and overweight status (body mass index [BMI] ≥ 25 kg/m²) by trial arm. We will summarize categorical variables as counts and percentages and continuous variables as means and standard deviations. The denominator for each percentage will be the number of participants within each treatment group, less any participants with missing data on the variable of interest. We will use *t*-tests and χ^2 tests to examine whether participants assigned to the trial arms differ on any continuous or categorical characteristics, respectively. We will report *p* values from these balance tests. Subsequent analyses will control for any unbalanced characteristics.

Analysis of the primary outcome (Efficacy analysis). We will use ordinary least squares regression (OLS) to examine whether the primary outcome differs by trial arm. Specifically, we will fit the following:

$$SSB \text{ calories purchased} = \beta_0 + \beta_1 \text{WARNING} + X\beta \quad (\text{Eq. 1})$$

Here, *SSB calories purchased* is the total calories from SSBs the participant had in her basket when she completed her shopping task, calculated as described in Table 2. WARNING is an indicator variable for whether the participant was in the health warning arm (WARNING = 1) or the control arm (WARNING = 0). We denote *X* as a vector of any participant characteristics (e.g., age, gender, race/ethnicity) found to be unbalanced across trial arms in balance tests.

The coefficient on WARNING (β_1) is the primary effect estimate, and gives the average difference in (adjusted) means between the treatment arm and the control arm. It is interpreted as the impact of SSB health warnings on total calories of SSBs purchased.

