- Mean product attitudes toward specific sugar-sweetened beverages
- Mean outcome expectations regarding consumption of beverages with added sugar

These regressions will take the general form of:

$$Y = \beta_0 + \beta_1 \text{WARNING} + X\beta \quad (\text{Eq. 3})$$

Here, WARNING and X are as defined previously and Y is the continuous secondary outcome. As above, the effect estimates are given by the coefficient on WARNING (β_1). This coefficient gives the average difference in (adjusted) means between the treatment arm and the control arm; it is interpreted as the impact of SSB health warnings on the secondary outcome being examined.

One of the secondary outcomes, number of SSBs purchased, is a count variable (i.e., takes on only nonnegative integer values) and is thus better evaluated with a count data model. To examine number of SSBs purchased, we will begin by fitting a Poisson regression:

$$\text{Prob}(y|\lambda) = \frac{e^{-\lambda}\lambda^y}{y!} \quad \text{for } y=0,1,2 \quad (\text{Eq. 4})$$

where

$$\lambda = e^{(\beta_1 \text{WARNING} + X\beta)} \quad (\text{Eq. 5})$$

WARNING is an indicator for treatment arm, X is a vector of any unbalanced participant characteristics and y is the observed number of SSBs purchased. Following the advice of Kennedy,⁶⁵ we will use robust standard errors to address the potential for overdispersion. We will test model fit using the Pearson goodness-of-fit test;⁶⁶ if the null hypothesis of a Poisson distribution is rejected, we will use a negative binomial regression in place of a Poisson regression. In either case, we will report the average differential effect of being in the health warning arm (vs. being in the control arm) on the predicted number of SSBs purchased.

Finally, the following secondary outcomes are dichotomous and will be assessed using logistic regression:

- Purchase of a sugar-sweetened beverage
- Noticing of the trial labels

These regressions will take the general form of:

$$Prob(Y = 1|WARNING, X) = \frac{e^{(\beta_1 WARNING + X\beta)}}{1 + e^{(\beta_1 WARNING + X\beta)}} \quad (\text{Eq. 6})$$

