WARNING and X are as defined previously, and Y is the dichotomous secondary outcome. For logistic regression results, we will report the average differential effect of being in the health warning arm (vs. being in the control arm) on the probability of the outcome occurring (i.e., probability the participant purchased a sugar-sweetened beverage), calculated using the method of recycled predictions.⁶⁶

Analysis of other outcomes. We will use OLS regression to examine differences by trial arm in the following other outcomes (all of which are continuously measured):

- Mean injunctive norms regarding consumption of beverages with added sugar
- Perceived message effectiveness of trial label
- Support for sugar-sweetened beverage health warning labels
- Mean self-efficacy to limit consumption of beverages with added sugar
- Mean response efficacy of limiting consumption of beverages with added sugar

To examine these outcomes, we will fit linear regressions of the general form:

$$Y = \beta_0 + \beta_1 WARNING + X\beta \quad (\text{Eq. 7})$$

WARNING and X are as defined previously and Y is the continuous other outcome. As above, the effect estimates are given by the coefficient on WARNING (β_1). This coefficient gives the average difference in (adjusted) means between the treatment arm and the control arm; it is interpreted as the impact of SSB health warnings on the outcome being examined.

Statistical software. Data preparation and analyses will be conducted in Stata Version 15.1 (StataCorp LLC, College Station TX).

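### Do Eqs. 5 and 6, printed without an intercept, distort the comparison with control for the count and yes/no secondary outcomes?

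*Combined protocol and SAP*

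**What the plan says.** Section 6.3 (Statistical Methods) gives seven numbered equations, six of which define a regression.

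- **Linear models.** Eq. 1, for the primary outcome, reads "SSB \text{ calories purchased} = \beta_0 + \beta_1 \text{WARNING} + X\beta \quad (\text{Eq. 1". Eq. 3, for continuous secondary outcomes, reads "Y = \beta_0 + \beta_1 \text{WARNING} + X\beta", and Eq. 7, for other outcomes, "Y = \beta_0 + \beta_1 WARNING + X\beta". Eq. 2, for moderation, also begins with β0.
- **Count model.** Eq. 4 gives the Poisson probability and Eq. 5 its mean, "\lambda = e^{(\beta_1 \text{WARNING} + X\beta". It covers the number of SSBs purchased. A negative binomial model replaces it if the Pearson goodness-of-fit test rejects the Poisson.
- **Logistic model.** Eq. 6 has "e^{(\beta_1 WARNING + X\beta)}}{1 + e^{(\beta_1 WARNING + X\beta" on its right-hand side. It covers purchase of an SSB and noticing the labels.
- **Covariates.** After Eq. 1, X is a "vector of any participant characteristics (e.g., age, gender, race/ethnicity) found to be unbalanced across trial arms in balance tests". After Eq. 5 the definition is repeated: "X is a vector of any unbalanced participant characteristics and y is the observed number of SSBs purchased".
- **Reported effect.** For the logistic outcomes it is "the average differential effect of being in the health warning arm (vs. being in the control arm) on the probability of the outcome occurring", obtained by recycled predictions. For the count outcome it is the corresponding difference in the predicted number of SSBs.

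**The concern.** β0 is absent wherever the exponent appears in Eqs. 5 and 6, and present in every linear model. It cannot be hidden in X: X holds only characteristics found to be unbalanced, it stands beside a separate β0 in the linear equations, and it may be empty.

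WARNING is 0 for control. Without an intercept, and with X empty, the control prediction is therefore a constant that owes nothing to the control data. The reported effect would compare the warning arm with that constant rather than with the randomised control group. For three secondary outcomes, two of them purchase behaviour, the estimate could be biased in either direction or have the wrong sign.

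**Working it through.** **Inputs.** From the documents: WARNING = 1 for the warning arm and 0 for control (Section 6.3); 200 per arm (Sections 3.3 and 6.4); two beverages chosen per participant, so the SSB count is 0, 1 or 2 (Section 4.2). The documents give no control-arm level for these three outcomes. Every arm value below is an assumption, and the plan has no figure of its own on this point to reproduce.

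**Step 1: literal reading, X empty.**

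- Eq. 5: control mean = exp(0) = 1. The warning mean is fitted freely, so the literal difference is (warning mean − 1). The true difference is (warning mean − control mean). Bias = control mean − 1.
- Eq. 6: control probability = exp(0)/(1 + exp(0)) = 0.5. By the same argument, bias = control proportion − 0.5.

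| Outcome (assumed control vs warning) | True difference | Literal difference |
|---|---|---|
| Any SSB, 70% vs 60% | −10 points | 60 − 50 = +10 points |
| Any SSB, 50% vs 40% | −10 points | 40 − 50 = −10 points |
| Any SSB, 40% vs 30% | −10 points | 30 − 50 = −20 points |
| Number of SSBs, 1.40 vs 1.20 | −0.20 | 1.20 − 1 = +0.20 |
| Number of SSBs, 1.00 vs 0.80 | −0.20 | 0.80 − 1 = −0.20 |
| Number of SSBs, 0.80 vs 0.60 | −0.20 | 0.60 − 1 = −0.40 |

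Fitting the first row to constructed data (140/200 vs 120/200) gives +10.0 points (p = 0.005) without a constant and −10.0 points (p = 0.037) with one.

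**Step 2: literal reading, X not empty (purchase 70% vs 60%).** The size of the error depends on what X contains.

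- One 0/1 characteristic, present in 50% of controls and 60% of the warning arm and unrelated to purchase: +1.9 points without a constant (p = 0.66, predicted control 57.5%); −10.0 points with one (p = 0.037, predicted control 70.0%).
- The same characteristic entered as a full set of indicators, one per category: −10.0 points without a separate constant, because the indicators sum to 1 and supply it.
- An age-like covariate (assumed control mean 29 to 36, SD 10 to 14, values below 18 set to 18, 2-year imbalance, unrelated to purchase): about −6.4 to −8.4 points instead of −10. The effect is attenuated, with no change of sign, because X = 0 lies far outside the data.

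The literal models are therefore biased in general. They are not biased when the control level happens to equal 1 or 0.5, or when X spans the constant.

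**Step 3: would the plan, followed as a whole, produce the literal fit?**

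- The text names standard models: Poisson, negative binomial and logistic regression. Nowhere does it say that the constant is suppressed.
- The result to be reported is a difference from the control arm. Recycled predictions set every participant to warning and then to control and average the two sets. That estimates the difference only if the control level has been estimated.
- Analyses are to be run in Stata, and regression software fits a constant unless told to leave it out.
- The equations are schematic. Eqs. 3, 6 and 7 are introduced as general forms, and the linear equations print no error term, yet nobody would read those as deterministic.

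With a constant fitted, the difference matches the true value in the refits above. In simulations of 200 replicates per scenario with 200 per arm, a true null was rejected in about 3% to 7.5% of replicates, in line with the nominal 5%.

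**The case for a change.** The best argument for a correction is that this document exists to fix the analyses before the data are examined, so its printed equations are the public record against which code will be checked. The omission is systematic: both non-linear models lack the term and all linear ones have it. A correct analysis would not match Eqs. 5 and 6 as printed. The negative binomial fallback has no mean equation of its own and would inherit Eq. 5. The repair is one symbol in each of two equations.

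The textual part of this stands. The term is missing, X does not supply it, and poor PDF extraction is an unlikely explanation because the term is absent at every occurrence. What does not follow is any effect on the results. To obtain the biased estimate an analyst would have to switch off the default constant and disregard the comparison with control that the same section asks for. Anyone checking code against the plan would meet that stated comparison directly after the equations. The sign reversals are arithmetically right, but they rest on assumed arm values and occur mostly with X empty.

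**Conclusion.** This is a clerical slip in notation and calls for no change to the plan. Eqs. 5 and 6 leave out the β0 that Eqs. 1, 2, 3 and 7 print, while the named models, the software and the reported difference from control already imply a fitted constant. Printing the term is harmless, and the expected change in any estimate is nil.

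The conclusion rests on one assumption: that the analyst fits ordinary Poisson, negative binomial and logistic models with their usual constant, as the prose describes. If the constant were deliberately suppressed, the bias with X empty would be the control mean minus 1 for the count, or the control proportion minus 0.5 for the two yes/no outcomes. It would generally be smaller with a continuous covariate such as age, and zero in the special cases shown above. Even then only three of the 14 secondary outcomes would be affected. The primary analysis, the other 11 secondary outcomes and the sample size do not depend on these equations.

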6.4 Sample Size and Power

The primary objective of this trial is to evaluate the effect of SSB health warnings on total calories of SSBs purchased. We used G*Power3 to determine sample size needs for

addressing this objective.⁶⁷ At the time of sample size determination, no studies of SSB health warnings had examined behavioral outcomes. Thus, we drew on effect sizes from studies of warnings' impact on intentions to purchase SSBs. These studies report medium^{17,19} or large¹⁸ effect sizes. To account for the intention-behavior gap, we powered the trial to detect an effect size between small and medium (standardized Cohen's $f^2 = 0.02$, i.e., trial arm will explain 2% of the total variance in SSB purchases).⁶⁸⁻⁷⁰ Using these specifications and a two-sided alpha of 0.05, we determined a necessary sample of 395 to detect an effect of $f^2 = 0.02$ or larger with 80% power. To account for potential missing data or incomplete study visits, we aimed to enroll 400 participants (200 in each arm).

6.5 Interim Analysis

No interim analyses were planned.

7 STUDY INTERVENTION

The intervention is exposure to a textual sugar-sweetened beverage health warning label. The health warning label is a 1.5" octagon with red background, a white border, and white text, as described in Section 1.2 above. In the health warnings arm, SSB health warning labels are adhered directly to the front-of-package of all SSB containers in the mock store.

8 SAFETY MANAGEMENT

To ensure the safety of participants, the principal investigator will monitor all data, including answers to free response survey questions, throughout the data collection period. No adverse events or medical emergencies are anticipated, as participants are completing questionnaires and completing normal activities of daily living (selecting products at a small store). Further, given the very low-risk nature of the study, there were no *a priori* criteria for stopping the entire study prematurely due to safety concerns or unexpected adverse events. The PI will monitor for any adverse events or medical emergencies and promptly report these to the sponsoring IRB following standard reporting procedures.

9 DATA COLLECTION AND MANAGMENT

Participant confidentiality will be protected throughout all phases of the research, including data collection, analysis, and publication of results. Other than to schedule participants for their study visit (for which contact information must be collected), this study does not collect any identifying information. All data (responses to survey questions, product selections made during the experiment) will be de-identified (i.e., will only be attached to identification codes, and not to any identifiable information). The key linking identification codes and respondent information will be kept in a locked file cabinet in a locked office and on a secure, password-protected computer/server. The key will be destroyed after data collection is complete.

10 RECRUITMENT STRATEGY

This study aims to recruit a convenience sample of 400 adults through a variety of methods our team has used to recruit diverse samples,⁷¹ including via community subject pools at the University of North Carolina, Chapel Hill (UNC) and Duke University, printed flyers posted in campus and community venues and distributed in-person on UNC and Duke campuses, and online advertisements on sites such as Craigslist and Facebook. Individuals who are interested in learning more about the study are invited to complete an online screening questionnaire. The screening questionnaire assesses the prospective participant's age, usual SSB consumption (using the BEV-Q 15, a validated questionnaire⁵⁷), and own and parental educational attainment. Eligible participants are English-speaking adults at least 18 years old who consume at least 12 ounces of SSBs per week.⁵⁷ Eligible potential participants will be invited to schedule a time to participate. Ineligible participants will be thanked for their time.

11 CONSENT PROCESS

This study obtains informed consent separately for the pre-enrollment screening questionnaire (screening phase) and for the in-person study visit (intervention phase).

For screening questionnaire, this study obtains informed consent via an online consent form with electronic agreement. The online consent form is presented to participants before they begin the online screening questionnaire. Participants are asked to read the form and indicate whether they agree to participate in the research. If they agree to participate, they select a button

labeled “I consent” and proceed with the survey. If they do not agree, the survey is ended and no information is collected.

For the in-person study visit, this study obtains written informed consent. When participants arrive for their study visit, the experimenter (the PI or a trained research assistant) escorts them to a private study room in the lab suite. The participant is provided with a copy of the consent document. The experimenter reviews the consent document with the participant and answers any questions the participant has. The document the general nature of the study, the risks and benefits of the study, and the general procedures used. After reviewing the document with the experimenter and asking any questions she may have, the participant indicates whether she agrees to participate. If the participant agrees to participate, both she and the experimenter sign and date a copy of the consent document. If the participant declines to participate, she is thanked and the study visit is ended.

The consent form for the in-person study visit uses incomplete disclosure. Specifically, the consent document gives general information about the study purpose (i.e., “a study about how consumers make choices in a naturalistic store setting”) but does not provide enough detail to reveal the main study objective. Participants are given truthful information about the study procedures in general terms (i.e., that they will be asked to select items in a shopping task and to complete a survey about their experience the store, attitudes and beliefs, and personal characteristics), including truthful information about the risks and benefits of participating in the study, but are not be fully informed about the study’s expected findings. After completing the study visit, participants are provided with a “Debriefing” form that provides details about the nature and purpose of the study. They are also given the opportunity to ask any questions they have about the study.

